5.1.5 Planned Trial Calendar

The following dates are approximate. The actual dates may differ as, for example, the trial will not start until all the appropriate regulatory and ethical approvals have been obtained.

Planned trial period - FVFS ^a to LVLS ^a :	April 2017 – February 2018
Planned inclusion period - FVFS ^a to FVLS ^a :	April 2017 – May 2017
Planned vaccination period:	April 2017 – June 2017
Planned follow-up period:	June 2017 – February 2018
Planned end of trial:	February 2018
Planned date of final clinical trial report:	July 2018

The expected trial duration is 7 months for all subjects included in the trial.

5.2 Enrollment and Retention of Trial Population

5.2.1 Recruitment Procedures

Before the start of the trial, the Investigator or delegate will contact an appropriate pool of potential subjects and invite them to participate in the study. The site will ensure that any advertisements used to recruit subjects (letters, pamphlets, posters) are submitted to the Sponsor prior to submission to the IRB for approval.

Recruitment procedures and materials will be submitted for IRB approval or favorable opinion before implementation.

5.2.2 Informed Consent Procedures

Informed consent is the process by which a subject voluntarily confirms his or her willingness to participate in a particular trial. Informed consent must be obtained before any study procedures are performed. The process is documented by means of a written, signed, and dated ICF.

In accordance with GCP, prior to signing and dating the consent form, the subject must be informed by appropriate study personnel about all aspects of the trial that are relevant to making the decision to participate, and must have sufficient time and opportunity to ask any questions.

The actual ICF used at each center may differ, depending on local regulations and IEC / IRB requirements. However, all versions must contain the standard information found in the sample ICF provided by the Sponsor. Any change to the content of the ICF must be approved by the Sponsor and the IEC / IRB prior to the form being used.

^a FVFS: first visit first subject LVLS: last visit last subject FVLS: first visit last subject

If new information becomes available that may be relevant to the subject's willingness to continue participation in the trial, this will be communicated to him / her in a timely manner. Such information will be provided via a revised ICF or an addendum to the original ICF.

Informed consent forms will be provided in duplicate, or a photocopy will be made. The original will be kept by the Investigator, and the copy will be kept by the subject.

Documentation of the consent process should be recorded in the source documents.

5.2.3 Screening Criteria

There are no screening criteria other than the inclusion and exclusion criteria.

5.2.4 Inclusion Criteria

An individual must fulfill *all* of the following criteria in order to be eligible for trial enrollment:

- 1) Aged 18 to <65 years on the day of inclusion^a
- 2) Informed consent form has been signed and dated
- 3) Able to attend all scheduled visits and to comply with all trial procedures
- 4) BMI: $18.5 \text{ Kg/m}^2 \leq \text{BMI} \leq 30 \text{ Kg/m}^2$

5.2.5 Exclusion Criteria

An individual fulfilling any of the following criteria is to be excluded from trial enrollment:

- 1) Subject is pregnant, or lactating, or of childbearing potential and not using an effective method of contraception or abstinence from at least 4 weeks prior to the first vaccination until at least 4 weeks after the last vaccination. To be considered of non-childbearing potential, a female must be post-menopausal for at least 1 year, or surgically sterile.
- 2) Participation at the time of study enrollment or, planned participation during the present trial period in another clinical trial investigating a vaccine, drug, medical device, or medical procedure
- 3) Receipt of any vaccine in the 4 weeks (28 days) preceding the first trial vaccination or planned receipt of any vaccine prior to V06
- 4) Previous vaccination against rabies (in pre- or post-exposure regimen) with either the trial vaccine or another vaccine
- 5) Receipt of immune globulins, blood or blood-derived products in the past 3 months
- 6) Known or suspected congenital or acquired immunodeficiency; or receipt of immunosuppressive therapy, such as anti-cancer chemotherapy or radiation therapy, within

^a "18 to <65 years" means from the day of the 18th birthday to the day before the 65th birthday. In states where the age of majority to consent to research is >18, inclusion criteria will be from the birthday acquiring the age of majority to the day before the 65th birthday.

the preceding 6 months; or long-term systemic corticosteroid therapy (prednisone or equivalent for more than 2 consecutive weeks within the past 3 months)

- 7) At high risk for rabies infection during the trial
- 8) Known systemic hypersensitivity to any of the vaccine or HRIG components, or history of a life-threatening reaction to the vaccines used in the trial or to a vaccine containing any of the same substances
- 9) Self-reported thrombocytopenia, contraindicating IM vaccination
- 10) Bleeding disorder, or receipt of anticoagulants in the 3 weeks preceding inclusion, contraindicating intramuscular vaccination
- 11) Deprived of freedom by an administrative or court order, or in an emergency setting, or hospitalized involuntarily
- 12) Current alcohol abuse or drug addiction
- 13) Chronic illness that, in the opinion of the investigator, is at a stage where it might interfere with trial conduct or completion
- 14) Moderate or severe acute illness/infection (according to investigator judgment) on the day of vaccination or febrile illness (temperature $\geq 100.4^{\circ}\text{F}$ [$\geq 38.0^{\circ}\text{C}$]). A prospective subject should not be included in the study until the condition has resolved or the febrile event has subsided
- 15) Identified as an Investigator or employee of the Investigator or study center with direct involvement in the proposed study, or identified as an immediate family member (i.e., parent, spouse, natural or adopted child) of the Investigator or employee with direct involvement in the proposed study
- 16) History of Guillain-Barré syndrome

5.2.6 Medical History

Prior to enrollment, subjects will be assessed for pre-existing conditions and illnesses, both past and ongoing. Any such conditions will be documented in the source document. Significant medical history (reported as diagnosis) including conditions for which the subject is or has been followed by a physician or conditions that could resume during the course of the study or lead to an SAE or to a repetitive outpatient care will be collected in the CRF. The significant medical history section of the CRF contains a core list of body systems and disorders that could be used to prompt comprehensive reporting, as well as space for the reporting of specific conditions and illnesses.

For each condition, the data collected will be limited to:

- Diagnosis (this is preferable to reporting signs and symptoms)
- Presence or absence of the condition at enrollment

The reporting of signs and symptoms is strongly discouraged.

Dates, medications, and body systems are not to be recorded, and the information collected will not be coded. Its purpose is to assist in the later interpretation of safety data collected during the trial.

5.2.7 Contraindications for Subsequent Vaccinations

5.2.7.1 Temporary Contraindications

Should a subject experience the condition below, the Investigator will postpone further vaccination until the condition is resolved.

- Febrile illness (temperature $\geq 100.4^{\circ}\text{F}$) or moderate or severe acute illness / infection on the day of vaccination, according to Investigator judgment

Postponement must still be within the timeframe for vaccination indicated in the [Table of Study Procedures](#). If any dose is delayed, the subsequent doses should be delayed according to the original time interval.

5.2.7.2 Definitive Contraindications

Should a subject experience one of the conditions listed below, the Investigator will discontinue vaccination:

- Pregnancy, as indicated by a positive urine test
- Anaphylactic or other significant allergic reaction to the previous dose of vaccine
- Immunoglobulin, blood or blood derived products received in the past 3 months or ongoing at the visit
- Immunosuppressive therapy such as anti-cancer chemotherapy or radiation therapy in the past 6 months or ongoing at the visit, or long-term systemic corticosteroid therapy (for more than 2 consecutive weeks in the past 3 months before the visit)
- HIV seropositivity
- Thrombocytopenia, bleeding disorder or receipt of anticoagulants contraindicating IM vaccination
- Administration of a vaccine other than the study vaccine between D0 and V06 (VAC5+14D)
- An SAE related to the trial vaccines following a vaccination.
- Any potential contact with rabies virus during the course of the study.
- Reporting of Guillain-Barré syndrome

Subjects will not be withdrawn due to contraindication but will be followed up for safety and possibly immunogenicity assessment.

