Planned Sample Size:	
A total of 320 subjects are to be enrolled:
 
Group 1 (VRVg-2, low dosage): n=80
 
Group 2 (VRVg-2, medium dosage): n=80
 
Group 3 (VRVg-2, high dosage): n= 80
 
Group 4 (VRVg-1): n= 40
 
Group 5 (Imovax Rabies, control): n= 40

Schedule of Study Procedures:	
Vaccination
 
All subjects will receive a total of five vaccine injections, one at D0, at D3, at D7, at D14 and at D28. In addition, all subjects will receive HRIG at D0.
 
Blood sampling
 
All subjects will provide five blood samples: one at D0, one at D14, one at D28, one at D42 and one at M7. Blood sampling will be done prior to each vaccine injection (and prior to both, vaccine injection and HRIG injection at D0).
 
Collection of safety data
 
Subjects will record information about solicited systemic reactions in a DC between the first and the second injections, between the second and the third injections, and during the 7 days following the remaining injections. Information about unsolicited systemic AEs will be recorded between each injection, and during the 28 days following the last injection. Solicited injection site reactions will be recorded in the DC in the 7 days after each injection, and unsolicited injection site reactions will be recorded during the 28 days after each injection. Subjects will record safety information in a Memory Aid (MA) from D56 (28 days following the last injection) until the end of the trial (M7).
 
Information about SAEs will be recorded throughout the trial.

Duration of Participation in the Trial:	The duration of each subject's participation in the trial will be approximately 7 months (28 days- vaccination period followed by 6 months -follow up period) except for prematurely discontinued subjects.
Investigational Product :	
The investigational product is VRVg: Purified Vero Rabies Vaccine - Serum Free (purified inactivated rabies vaccine prepared on Vero cell line)
 
VRVg-2 is the modified formulation.
 
VRVg-1 is the initial formulation.

Form:	Freeze-dried

Composition:	Each 0.5 mL dose of either VRVg-2 or VRVg-1 contains Rabies Virus – Wistar Rabies Pitman Moore/WI 38 1503-3M strain: ≥ 2.5 IU (potency; NIH) and the components specified in the following table: [REDACTED] [REDACTED]
Route:	Intramuscular (IM)
Batch Number:	Batch numbers are to be determined

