5.1.3 Trial Plan

The trial plan is summarized in the [table of study procedures](#).

Recruitment and information of subjects:

Before inclusion in the trial, the Investigator will orally inform potentially eligible subjects about the trial. They will be given an oral description of the trial design, presenting the general benefits and risks related to the trial. They will be informed that they may return and receive further information and sign the full informed consent during the recruitment period. The process of subject recruitment and any oral or written information that will be provided to the subjects must be documented. This will be available in the Investigator's file and the Trial Master File.

It should be noted that subjects who may have been pre-screened may not necessarily be included in the trial if the required number of subjects have already been recruited.

Informed consent will be obtained before inclusion of the subject in the study (see [Section 5.2.2](#)).

Trial description:

After having signed the ICF and provided the initial blood sample, eligible subjects will be included in the study.

Eligible subjects will receive a total of 5 injections (1 injection at D0, D03, D07, D14 and D28) according to the Essen regimen for rabies post-exposure prophylaxis (PEP). HRIGs will be administered at D0 at the time of the first vaccine injection.

Subjects will be observed for safety for 30 minutes after each vaccination, and any AE/reaction occurring between each vaccination and up to 28 days after the fifth vaccination will be recorded by the subjects in a diary card (DC). The Investigator or delegate will transcribe the DC information into the electronic case report form (CRF) after interviewing the subject. In addition, all SAEs and AESIs will be recorded throughout the study, i.e., up to 6 months after the last injection.

Immunogenicity will be assessed in all subjects included in the trial, before the first vaccine injection (VAC1) (D0), before VAC4 (D14), before VAC5 (D28), 14 days after VAC5 (D42) and 6 months after VAC5 (M7). The RFFIT assay will be used for immunogenicity assessment.

Blood sampling:

All subjects will provide a total of five blood samples of 5-mL each, to assess the immune response induced by the rabies vaccines.

Table 5.3 below outlines the schedule of blood sampling and vaccine injection.

Table 5.3: Blood Sampling and Vaccination Schedule

	V01	V02	V03	V04	V05	V06	V07	V08

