- 14) Remind the subject to bring back the Diary card when they return for V02 at a specified date and time.
- 15) Remind the subject to notify the site in case of an SAE or pregnancy (for woman of childbearing potential).
- 16) Complete the relevant source document information and CRF pages for this visit.

V02 (3 days after VAC1): Collection of Safety Information and Vaccination

- 1) Review the DC1 with the subject, including any adverse events, medications, or therapy that occurred since vaccination by Investigator or delegate. The subject will continue using the DC1 to collect safety information until the V04.
- 2) Urine pregnancy test, if applicable.
- 3) Conduct a physical examination, including temperature.

- 4) Check contraindication for subsequent vaccinations (see [Section 5.2.7](#)).
- 5) Call the Interactive Response Technology (IRT) system (IV/WRS) for randomization, dose number assignment and allocation of subject number (see [Section 6.6](#)).
- 6) Inject the appropriate study vaccine (VAC2) in the opposite arm as compared to the VAC1.
- 7) Keep the subject under observation for 30 minutes, and record any adverse reaction in the source document.
- 8) Remind the subject to bring back the Diary card when they return for V03 at a specified date and time.
- 9) Remind the subject to notify the site in case of an SAE or pregnancy (for woman of childbearing potential).
- 10) Complete the relevant source document information and CRF pages for this visit.

V03 (7 [+1] days after VAC1): Collection of Safety Information and Vaccination

- 1) Review the DC1 with the subject, including any adverse events, medications, or therapy that occurred since vaccination by Investigator or delegate. The subject will continue using the DC1 to collect safety information until V04.
- 2) Urine pregnancy test, if applicable.
- 3) Conduct a physical examination, including temperature.
- 4) Check contraindication for subsequent vaccinations (see [Section 5.2.7](#)).
- 5) Call the Interactive Response Technology (IRT) system (IV/WRS) for randomization, dose number assignment and allocation of subject number (see [Section 6.6](#)).
- 6) Inject the appropriate study vaccine (VAC3) in the opposite arm as compared to the VAC2.
- 7) Keep the subject under observation for 30 minutes, and record any adverse reaction in the source document.
- 8) Remind the subject to bring back the Diary card when they return for V04 at a specified date and time.

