6.3 Identity of Other Product

Licensed HRIGs (Imogam® Rabies) will be administered at D0 in all subjects included in the trial for simulated post-exposure treatment.

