6.3.1 Composition

- Human rabies immunoglobulins 150 IU/mL (commercial batch to be determined)

The recommended dose is 20 IU/kg (or 9 IU/lb) of body weight.

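### Protocol 5.2.7.2 stops vaccination after immunoglobulin in the past 3 months, but every subject receives HRIG at D0 and is scheduled for four more injections

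*Protocol*

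**What the plan says.** Protocol 5.2.7.2 (Definitive Contraindications) is mandatory: if a listed condition arises, "the Investigator will discontinue vaccination". The list includes "Immunoglobulin, blood or blood derived products received in the past 3 months or ongoing at the visit". Another item in the same list reads "Administration of a vaccine other than the study vaccine between D0 and V06".

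Protocol 6.3 states: "Licensed HRIGs (Imogam® Rabies) will be administered at D0 in all subjects included in the trial for simulated post-exposure treatment". Section 6.3.1 gives the composition of that product as "Human rabies immunoglobulins 150 IU/mL", and 5.1.3 fixes the timing: "HRIGs will be administered at D0 at the time of the first vaccine injection". The Synopsis sets the vaccine schedule: "All subjects will receive a total of five vaccine injections, one at D0, at D3, at D7, at D14 and at D28".

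Protocol 5.1.4 includes at V02, V03, V04 and V05 the step "Check contraindication for subsequent vaccinations", with a reference to Section 5.2.7, and places it before the injection. The Table of Study Procedures has definitive contraindications collected up to V05 or throughout the trial. Protocol 6.8 repeats the immunoglobulin item, in the same words, among the category 2 reportable medications, which it ties to the definitive contraindications.

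**The concern.** A site that follows 5.2.7.2 to the letter must stop vaccination at V02 in every subject, because each has received an immunoglobulin three days earlier. A site that follows the schedule gives VAC2 to VAC5 against the text of 5.2.7.2.

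Two things are at stake:

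- **Conduct.** A subject stopped at V02 would miss VAC2 to VAC5, would leave the per-protocol set (PPAS) for not having the first three doses (SAP 5.2.2), and would stay in the full analysis set (FAS), which needs only one dose (SAP 5.2.1).
- **The record.** Definitive contraindications are collected data. As worded, the immunoglobulin item could be recorded as met by every subject, or only by subjects who received immunoglobulin from outside the trial.

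**Working it through.** The plan states no figure on this point to reproduce. The check compares the interval from HRIG to each contraindication check with the 3-month look-back, and then counts the injections concerned.

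**Inputs**

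- HRIG at D0 in all subjects (Protocol 5.1.3, 6.3).
- Visit windows after VAC1 (Protocol 5.1.4 and Table of Study Procedures): V02 at 3 days; V03 at 7 (+1); V04 at 14 (±1); V05 at 28 (±3).
- Look-back of 3 months (Protocol 5.2.7.2): 89 to 92 days by calendar, or 84 days if read as 12 weeks.
- 320 subjects, 5 injections each (Synopsis): 3 × 80 + 2 × 40 = 320.

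**Days from HRIG to each check**

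| Visit | Injection due | Days since HRIG | Within 84 days? |
|---|---|---|---|
| V02 | VAC2 | 3 | yes |
| V03 | VAC3 | 7 to 8 | yes |
| V04 | VAC4 | 14 − 1 to 14 + 1 = 13 to 15 | yes |
| V05 | VAC5 | 28 − 3 to 28 + 3 = 25 to 31 | yes |

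The longest interval is 31 days, well short of even the 84-day reading. Every subject therefore meets the item at all four checks.

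**Injections covered by the literal rule**

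- Planned: 320 × 5 = 1,600.
- Due after HRIG has been given: 320 × 4 = 1,280.
- Share: 1,280 / 1,600 = 80%.

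**Does any other text remove the conflict?**

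- *Exemption of trial products.* The vaccine item in 5.2.7.2 excepts the study vaccine in so many words. The immunoglobulin item carries no such exception, nor does its copy in 6.8. The list therefore does not treat trial products as outside its scope by default.
- *Exclusion criterion 5.* It uses a similar 3-month look-back (Protocol 5.2.5) but is not in conflict. At V01 eligibility is step 7 and HRIG is step 11, so the criterion is applied before HRIG is given.
- *PPAS definition.* SAP 5.2.2 excludes subjects who received category 2 products between D0 and D14, but it confines this to restricted products and to relevant protocol deviations. HRIG given as planned is neither, so category 2 does not empty the PPAS. Those limiting words do not appear in 5.2.7.2.
- *Elsewhere.* Neither the protocol nor the SAP contains text exempting the study HRIG from 5.2.7.2.

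**The case against.** The strongest reply is that only one reading is workable. HRIG followed by four more injections is the trial's design: 5.1.2 gives HRIG co-administration as part of the rationale, and the PPAS excludes a subject who did *not* receive the correct HRIG amount or the first three doses. A general contraindication list cannot sensibly cancel the regimen under study. Its opening words also suit events that befall a subject better than a procedure applied to everyone. On this view a short exempting phrase is missing, no site would be misled, and the 80% counts injections under a reading nobody would use. It can be added that 6.8 deals with concomitant medication while 6.3 classes HRIG as a trial product, and that an amendment may come too late: vaccination was planned for April to June 2017, and SAP 5.6 describes the data review partly in the past tense.

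Much of this stands. The intent is plain, the practical effect is probably nil, and the 80% measures the reach of the wording, not an expected effect. The documents do not settle whether vaccination was already complete.

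It does not remove the contradiction. The item is an explicit look-back, HRIG is given after eligibility has been confirmed, and the neighbouring item shows that an exemption was written where one was wanted. Section 6.8 repeats the item and links it to the definitive contraindications, so correcting 5.2.7.2 alone would leave the same wording in force there.

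**Conclusion.** The concern holds. Protocol 5.2.7.2 and the HRIG and vaccination schedule contradict each other as worded, for all 320 subjects at each of four visits (1,280 of 1,600 planned injections). This rests on the literal text and the protocol's visit windows. It does not depend on how 3 months is counted, since 31 days is inside any reading.

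The documents give no number of subjects who would actually be stopped. It is probably none, and no rate is assumed. If all sites follow the schedule, no change to FAS or PPAS results or to the dosage choice is expected. The passages should still be corrected, because a mandatory rule for stopping vaccination, checked at four visits, would halt the trial's own regimen if followed exactly.

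**What to change.** The sponsor should reconcile the immunoglobulin item in Protocol 5.2.7.2, and its copy under category 2 in 6.8, with the HRIG and vaccination schedule in 5.1.3, 5.1.4 and 6.3. Which clinical rule stands is the sponsor's decision, and none is proposed here. SAP 5.2.2 refers to category 2 and would follow the reconciled wording, so it needs no change of analysis.

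The cost is wording in two protocol sections, with no data or programming work. It can go into the next amendment, which under Protocol 5.4 needs IEC/IRB approval even if it is administrative. If vaccination is already complete, reconciliation can no longer affect conduct, but it would still settle how the recorded definitive contraindications are to be read.
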